## **2. STUDY OBJECTIVES AND HYPOTHESIS**

### **2.1. Study Objectives**

#### **2.1.1. Primary Objective**

The primary objective of this study is:

- To determine the plasma PK of pexidartinib after a single oral dose of 200 mg in subjects with moderate HI compared to that in healthy subjects with normal hepatic function

#### **2.1.2. Secondary Objectives**

The secondary objectives of this study are:

- To assess the safety and tolerability of pexidartinib after a single oral dose of 200 mg in subjects with normal and moderately impaired hepatic function
- To determine the PK of ZAAD-1006a in subjects with moderate HI, compared to that in healthy subjects with normal hepatic function
- To assess protein binding of pexidartinib and ZAAD-1006a in moderate HI, compared to that in healthy subjects with normal hepatic function

### **2.2. Study Hypothesis**

This is not a hypothesis testing study. This study will estimate the effect of moderate hepatic dysfunction on the PK of pexidartinib and ZAAD-1006a, compared to a group of healthy subjects with normal hepatic function.

### **2.3. Study Endpoints**

#### **2.3.1. Primary Endpoints**

##### **Pharmacokinetic Endpoints**

- Pexidartinib: Plasma Cmax, Tmax, AUClast, AUCinf, Kel, t1/2, CL/F, Vz/F, and protein binding
- ZAAD-1006a: Plasma Cmax, Tmax, AUClast, AUCinf, t1/2, MPR based on AUClast and AUCinf, and protein binding

The following unbound PK parameters will be calculated for both pexidartinib and ZAAD 1006a:

- Cmax
- Tmax
- AUClast
- AUCinf

PL3397-A-U129 Protocol  
Version 2.0, 10 DEC 2019

- t1/2

And also for pexidartinib:

- CL/F
- Vz/F

### **2.3.2. Secondary Endpoints**

#### **Safety Endpoints**

- AEs
- Vital signs
- 12-lead ECGs
- Clinical laboratory tests

### **2.3.3. Exploratory Endpoint**

Not applicable

[figure not shown]
### 3. STUDY DESIGN

#### 3.1. Overall Design

##### 3.1.1. Overview

This is a Phase 1, open-label, 1-treatment, 1-period study conducted in healthy subjects with normal hepatic function and in subjects with moderate hepatic impairment. An overview of the study is depicted in Figure 3.1 below:

**Figure 3.1: Overview of study design**

Abbreviations: D = Day; PK = pharmacokinetics

Screening will occur within 21 d of Check-in (Day -2) at the clinic, and eligible individuals will be confined at the clinic starting on Day -2 for approximately 8 d. All subjects will be given a single dose of pexidartinib (1 × 200-mg capsule) orally on Day 1 with 240 mL of water. Subjects will fast for at least 10 h before pexidartinib dosing and will continue to fast for at least 4 h after pexidartinib administration. Water will be allowed ad libitum up to 1 h prior to dosing and resuming at 2 h after pexidartinib administration.

Subjects will check out from the clinic on Day 8 of the study following completion of the final blood collection and Check-out procedures.

Details for each study visit are provided in the study procedures section (see Section 6) and the Schedule of Events table (see Appendix 16.5).

##### 3.1.2. Dose Escalation Process

Not applicable

### **3.1.3. Study Stopping Criteria**

Not applicable

## **3.2. Discussion of Study Design**

The purpose of this study is to assess the effect of moderate HI on the PK of pexidartinib. The study will consist of 8 subjects with moderate HI and 8 matched controls. The severity of HI will be assessed by the NCI-ODWG group TBIL >1.5 to 3x ULN, not due to Gilbert's syndrome. Subjects with normal hepatic function will be matched to subjects with moderate HI according to sex, age ( $\pm 10$  years [y]), and weight ( $\pm 20\%$ ) based on mean values. Subjects with HI will be recruited first. Healthy subjects with normal liver function will be enrolled after all subjects with moderate HI have received study drug.

A single 200-mg dose of pexidartinib (1  $\times$  200-mg capsule) was chosen based on the safety profile and with an assumption that moderate hepatic impairment may double the exposure. The open-label, single dose study design is appropriate for this Phase 1 study.

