This is a Phase 1, open-label, single dose PK study in male and female subjects with normal and moderately impaired hepatic function. The study will consist of 8 subjects with moderate HI and matched controls (8 healthy subjects with normal hepatic function). The severity of HI will be assessed by the NCI-ODWG criteria to identify subjects with moderate HI for enrollment in this study. The cohort of subjects with normal hepatic function will be group matched to subjects with moderate HI according to sex, age ( $\pm 10$  years [y]), and weight ( $\pm 20\%$ ) based on mean values. Subjects with moderate HI will be recruited first. Healthy subjects with normal hepatic function will be enrolled after all moderate HI subjects have received study drug.

Subjects will be screened within 21 days (d) prior to the administration of study drug. Subjects will be admitted to the clinical unit on Day -2 and will remain domiciled until the completion of all study procedures approximately 168 hours (h) after oral administration of 200 mg pexidartinib (1  $\times$  200-mg capsule). Study drug will be administered on Day 1 in the morning following an overnight fast of 10 h. Water consumption will be restricted from 1 h predose to 2 h post dose, except for the specified amount that is to be administered with study drug. Fasting will continue until 4 h after study drug administration.

Serial blood samples will be collected for PK analysis of pexidartinib and ZAAD-1006a at predose (within 30 minutes [min] prior to dosing) and at 0.5, 1, 1.5, 2, 2.5, 3, 3.5, 4, 4.5, 5, 6, 8, 10, 12, 24, 36, 48, 72, 96, 120, 144, and 168 h post dose.

Plasma will be harvested and analyzed for the quantification of pexidartinib using a validated liquid chromatography-tandem mass spectrometry method. ZAAD-1006a will be analyzed using a qualified liquid chromatography-tandem mass spectrometry assay.

---

PL3397-A-U129 Protocol  
Version 2.0, 10 DEC 2019

---

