**Safety Endpoints**

Pexidartinib safety and tolerability will be assessed by:

- AEs
- Vital signs
- 12-lead ECGs
- Clinical laboratory tests

---

**Planned Sample Size:** Sixteen subjects will be enrolled; 8 will have moderate HI and 8 will be healthy subjects with normal hepatic function who are group matched to subjects in the HI group by age, sex, and body weight.

---

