### 4.1. Inclusion Criteria

Subjects must satisfy all of the following criteria to be included in the study:

1. Male and female subjects 18 y to 75 y of age (inclusive), with a body mass index (BMI) of 18 kg/m^2 to 40 kg/m^2 (inclusive) at Screening.
2. Female subjects who are of non-childbearing potential must be:
  - a. Surgically sterile (ie, bilateral tubal ligation or removal of both ovaries and/or uterus at least 6 mo prior to dosing, or Essure® with hysterosalpingogram [documentation to confirm tubal occlusion 12 wk after procedure]).
  - b. Naturally postmenopausal (spontaneous cessation of menses) for at least 12 consecutive mo prior to dosing, confirmed by follicle stimulating hormone (FSH) testing or estradiol testing.
3. Female subjects who are of childbearing potential must agree to nonhormonal methods of contraceptive therapy or refrain from sexual intercourse to prevent pregnancy until 1 mo postdose. If the subject is on oral contraceptive, the subject also needs to use a nonhormonal method in addition to oral contraceptive. Female subjects must refrain from breastfeeding for at least 2 weeks post dose.
4. Male subjects must agree to use a condom and spermicide during sexual intercourse until 1mo post dose or must have had a vasectomy and must be willing not to donate sperm until 1 mo post dose.
5. All subjects must agree not to donate blood, plasma, platelets, or any other blood components from Screening to 4 wk post dose.
6. All subjects must be willing to refrain from consuming grapefruit/grapefruit juice, Seville oranges, and pomegranates/pomegranate juice 10 d before the dose of study drug is given on Day 1 until End-of-Study (EoS).
7. All subjects must provide written informed consent prior to participating in the study.
8. Subjects with HI are required to have:
  - a. Documented history of chronic liver disease diagnosed by ultrasonography, computed tomography scan, liver biopsy, or magnetic resonance imaging or history of chronic (>6 mo) hepatitis B virus (HBV) or hepatitis C virus (HCV) infection
  - b. Moderate HI as assessed by NCI-ODWG criteria [total bilirubin (TBIL) >1.5 to 3x ULN (not due to Gilbert's syndrome)] and confirmed at Check in.

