12. Loss of more than 450 mL blood during the 3 mo before the trial (eg, as a blood donor)
13. Current enrollment in or have not yet completed at least 30 d or 5 elimination half-lives, whichever is longer, since receiving an investigational device or product, or receipt of other investigational agents within 30 d of pexidartinib
14. History of any malignancy (except basal cell carcinoma) in the past 5 y

15. In the opinion of the investigator, history of a clinically significant illness within 4 wk prior to administration of study drug
16. Participation in a previous pexidartinib study
17. Employment by the clinic or the Sponsor
18. Any other reason, in the opinion of the investigator, which precludes subject participation in the study
19. Familial relationship with another study participant

Additional Exclusion Criteria for Matched Healthy Subjects:

1. Any clinically relevant abnormality identified on the physical examination, ECG, vital signs, or laboratory tests at Screening.
2. Any clinically unstable, uncontrolled medical condition.
3. Liver function (AST, ALT, alkaline phosphatase of liver origin, and TBIL) test results above the upper limit of normal at Screening and on Day -2.
4. Use of any prescription or over-the-counter (OTC) medications (systemic or topical), vitamins, or dietary/herbal supplements within 14 d prior to study drug dosing, with the exception of acetaminophen ( $\leq 2$  g/d), stool softeners, and topical hydrocortisone cream, which are permitted.

Additional Exclusion Criteria for Subjects with Hepatic Impairment:

1. Any clinically unstable, uncontrolled medical conditions other than those associated with HI.
2. Evidence of infection with HBV and/or new or acute HCV infection within the preceding 6 mo.
3. HI subjects maintained on a gastric pH modifier (eg, proton pump inhibitor), must be discontinued from this medication 7 d prior to and 24 h after pexidartinib administration. The subject should be switched to Gelusil (aluminum hydroxide, magnesium hydroxide, and simethicone) as needed for up to 48 h prior to the administration of pexidartinib. Gelusil use is prohibited from 48 h prior to the administration of pexidartinib to 24 h post pexidartinib dosing. At 24 h post pexidartinib, treatment with the usual gastric pH modifier can be resumed.

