#### **5.1.2. Method of Treatment Allocation**

Subjects with HI will be recruited first. When all moderate HI subjects have received study drug, the group of healthy subjects with normal hepatic function can be enrolled. There is no randomization in this study.

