### **10.5. Sample Size Determination**

Sixteen subjects will be enrolled. Half of these subjects will be moderate HI and the other half will be healthy subjects with normal hepatic function matched by age, gender, and body weight. The sample sizes are not based on statistical considerations. The number of subjects is considered sufficient to achieve the study objectives (see FDA Guidance 2003). Subjects who discontinue after receiving study drug will not be replaced unless approved by the sponsor.

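### Does the control-matching rule need rewriting because it could bind each control or only the group mean, and sets no tolerance for sex?

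*Combined protocol and SAP*

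**What the plan says.** The matching rule appears in four places in the protocol.

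- Synopsis, Study Design: "The cohort of subjects with normal hepatic function will be group matched to subjects with moderate HI according to sex, age" (±10 years) and weight (±20%), on mean values.
- Synopsis, Planned Sample Size: the healthy subjects are "group matched to subjects in the HI group by age, sex, and body weight", without windows.
- Section 3.2: "Subjects with normal hepatic function will be matched to subjects with moderate HI according to sex, age" and weight, with the same two windows, "based on mean values. Subjects with HI will be recruited first".
- Section 10.5: "healthy subjects with normal hepatic function matched by age, gender, and body weight", without windows.

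Section 4.2 has a list headed "Additional Exclusion Criteria for Matched Healthy Subjects", but none of its four items concerns matching. The only age and size limits in Section 4.1 apply to everyone: "Male and female subjects 18 y to 75 y of age (inclusive), with a body mass index (BMI) of 18" to 40 kg/m². Section 5.1.2 fixes the order of enrolment: "When all moderate HI subjects have received study drug, the group of healthy subjects with normal hepatic function can be enrolled". Section 10.4.1 compares the hepatic impairment (HI) group with the matched controls by analysis of variance and reports geometric least squares means, their ratio and a 90% interval. It names no covariate.

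**The concern.** The study is not randomised and has 8 subjects per group. Section 1.3 says its findings will help with dose recommendations in moderate HI. If the healthy volunteers differ from the HI group in age, sex or weight, part of that difference could pass into the exposure ratio. Matching is the only step in the protocol aimed at those three factors.

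The wording of that step is uneven. Section 3.2 drops the word group, and Section 10.5 drops the windows as well. A tolerance around a mean has no direct meaning for sex, so on a literal reading none of the nine possible male/female splits among 8 controls is excluded. With up to 3 sites, no one is named to work out the HI means or to confirm the match. A volunteer could meet all of Section 4 and still lie far from the HI group in age or weight.

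**Working it through.** **The plan's own figure.** There is none to reproduce. Section 10.5 says the 8 per group is not derived statistically, and no SD, CV or weight effect is given.

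**The four statements side by side.**

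| Place | Says group | Gives windows | Tied to means |
|---|---|---|---|
| Synopsis, Study Design | yes | yes | yes |
| Synopsis, Planned Sample Size | yes | no | no |
| Section 3.2 | no | yes | yes |
| Section 10.5 | no | no | no |

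Both places that give windows tie them to means, and none of the four describes pairs or a check of each subject. The shorter statements omit detail but contradict nothing. The reading that fits all four is that the control-group mean lies within 10 years and 20% of the HI-group mean.

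**How far the readings differ.** Suppose the HI mean weight is 80 kg (assumed).

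- Controls of 50, 55, 60, 70, 90, 100, 105 and 110 kg have mean 640/8 = 80 kg, so they pass as a group.
- The window for one subject is 0.8 × 80 = 64 kg to 1.2 × 80 = 96 kg. Only 2 of the 8 lie inside it.

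For age, with an assumed SD of 10 years:

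- The difference between two means of 8 has SD 10 × √(2/8) = 5 years, so 95% of unselected groups pass.
- One control against the HI mean has SD 10 × √(1 + 1/8) = 10.6 years, so 65% of individuals pass.

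**What this does to the ratio.** All inputs are assumptions: log-weight SD 0.22; residual CV 35%, so residual log SD = √ln(1 + 0.35²) = 0.340; AUC proportional to weight^(−b), with b from 0 to 1; whole groups (mean rule) or single controls (each-control rule) redrawn until the rule is met. Simulation with 60,000 runs per case gives:

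| Control source | Rule | Ratio shift at b = 1 | 90% interval coverage, b = 0 to 1 |
|---|---|---|---|
| Same weights as HI | group mean | under 1% | 0.90 to 0.91 |
| Same weights as HI | each control | under 1% | 0.90 to 0.92 |
| 20% heavier | group mean | 1.12 | 0.90 down to 0.88 |
| 20% heavier | each control | 1.05 | 0.90 to 0.92 |
| 20% lighter | group mean | 0.86 | 0.90 down to 0.84 |
| 20% lighter | each control | 0.95 | 0.90 to 0.91 |

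At b = 0 there is no shift in any row. The worst a compliant group mean can do is sit on the edge of the window. That multiplies the ratio by 1.2^b (at most 1.20) or 0.8^b (at least 0.80).

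**Scale.** With 14 degrees of freedom, t(0.95) = 1.761. The interval factor is exp(1.761 × 0.340 × √(2/8)) = exp(0.299) = 1.35. On the log scale, the largest simulated shift is |ln 0.86| = 0.151, about half of 0.299.

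**Weight adjustment.** Under the mean rule with one weight population, the root mean squared error of the log ratio is 0.170 without adjustment and 0.175 with it at b = 0. At b = 1 the figures are 0.195 and 0.175. Adjustment costs a little if weight does not matter and helps if it matters strongly, and the documents do not say which holds.

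**The case for a change.** The best case for a change is that an enrolment rule should be explicit before the first control is dosed. Section 10.6 requires the SAP only before database lock, so it may come too late to set that rule. Under the group-mean reading the weight gap can also be appreciable: with one weight population it exceeds 10% in 33% of simulated studies, against 2% if each control must match. Even if the group-mean reading is accepted, sex has no tolerance and no one is assigned to confirm the match.

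The last two points stand as omissions of detail, and so does the uneven wording. The rest carries less weight.

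- Absence from Section 4 is not clearly a defect. That section lists conditions that one subject passes or fails, and under a group-mean rule no single control does either.
- Matching is not the only guard against confounding. Sections 4.1, 4.2, 5.6 and 5.6.1 restrict or standardise renal function, enzyme inhibitors and inducers, smoking, gastric pH modifiers, fasting and meals. Matching is the only stated guard for age, sex and weight relative to the HI group.
- Database lock is the latest date for the SAP, not its actual date.
- Controls enrol after every HI subject has been dosed, so the HI means and sex split are known and recruitment can be steered towards them. The simulation does not credit this.
- Section 10.3 summarises age, weight, BMI and sex by group, so any imbalance will be visible beside the ratio.
- Geometric least squares means for two groups already imply a log-scale model with a group term.

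**Conclusion.** No change to the plan follows. The rule is worded unevenly, but its natural meaning can be recovered, and enrolling the HI group first makes it workable. For sex, study staff would sensibly aim for a similar number of men and women in the two groups; the lack of a numerical tolerance is missing detail that they can supply.

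If both groups come from one weight population, either reading leaves the 90% interval near its nominal level and bias below 1%. Material bias needs three things together: a control source that differs in weight by about 20%, a strong effect of weight on exposure, and recruitment that ignores known HI values. Even then the lowest coverage found is 0.84, at b = 1 with a lighter source. These figures rest on an assumed log-weight SD of 0.22 and CV of 35% and model AUC only; the documents neither support nor exclude them. Asking which reading applies would record a choice without improving on it. A weight-adjusted sensitivity analysis would leave the primary result as it is, and the SAP can add one without a change to the protocol.

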## 4. STUDY POPULATION

All subjects must sign an Informed Consent Form (ICF) provided by the site.

### 4.1. Inclusion Criteria

Subjects must satisfy all of the following criteria to be included in the study:

1. Male and female subjects 18 y to 75 y of age (inclusive), with a body mass index (BMI) of 18 kg/m^2 to 40 kg/m^2 (inclusive) at Screening.
2. Female subjects who are of non-childbearing potential must be:
  - a. Surgically sterile (ie, bilateral tubal ligation or removal of both ovaries and/or uterus at least 6 mo prior to dosing, or Essure® with hysterosalpingogram [documentation to confirm tubal occlusion 12 wk after procedure]).
  - b. Naturally postmenopausal (spontaneous cessation of menses) for at least 12 consecutive mo prior to dosing, confirmed by follicle stimulating hormone (FSH) testing or estradiol testing.
3. Female subjects who are of childbearing potential must agree to nonhormonal methods of contraceptive therapy or refrain from sexual intercourse to prevent pregnancy until 1 mo postdose. If the subject is on oral contraceptive, the subject also needs to use a nonhormonal method in addition to oral contraceptive. Female subjects must refrain from breastfeeding for at least 2 weeks post dose.
4. Male subjects must agree to use a condom and spermicide during sexual intercourse until 1mo post dose or must have had a vasectomy and must be willing not to donate sperm until 1 mo post dose.
5. All subjects must agree not to donate blood, plasma, platelets, or any other blood components from Screening to 4 wk post dose.
6. All subjects must be willing to refrain from consuming grapefruit/grapefruit juice, Seville oranges, and pomegranates/pomegranate juice 10 d before the dose of study drug is given on Day 1 until End-of-Study (EoS).
7. All subjects must provide written informed consent prior to participating in the study.
8. Subjects with HI are required to have:
  - a. Documented history of chronic liver disease diagnosed by ultrasonography, computed tomography scan, liver biopsy, or magnetic resonance imaging or history of chronic (>6 mo) hepatitis B virus (HBV) or hepatitis C virus (HCV) infection
  - b. Moderate HI as assessed by NCI-ODWG criteria [total bilirubin (TBIL) >1.5 to 3x ULN (not due to Gilbert's syndrome)] and confirmed at Check in.
  - c. Normal or clinically nonrelevant findings at physical examination and normal limits or clinically nonrelevant deviations in clinical laboratory evaluations, with exception of findings that in the opinion of investigator are consistent with subject's HI.
9. Creatinine Clearance  $\geq$  70 mL/min estimated using the Cockcroft Gault formula without any markers of chronic kidney disease at Screening and Check-in.
10. Clinical stability in the opinion of the investigator

## 4.2. Exclusion Criteria

Subjects who meet any of the following criteria will be disqualified from entering the study:

1. Clinically relevant abnormal history, physical findings, ECG, or laboratory values at the Screening assessment that could interfere with the objectives of the study or the safety of the subject
2. Subjects with primary biliary cirrhosis or primary sclerosing cholangitis
3. Concomitant medication (moderate or strong inhibitor or inducer of CYP3A4 [eg, itraconazole, rifampin], CYP2C9 [eg, fluconazole, carbamazepine] and UGT [eg, probenecid, rifampin]) within 2 wk before dosing and throughout study
4. History of stomach or intestinal surgery or resection that would potentially alter absorption and/or excretion of orally administered drugs (with the exception of appendectomy, hernia repair, and/or cholecystectomy)
5. Presence or history of severe adverse reaction to any drug (except penicillin)
6. A positive drugs of abuse screen (unless the drug is medically prescribed by a licensed health care provider) or alcohol breath test at Screening or at Check-in on Day -2 or a subject who will not agree to smoke  $\leq 10$  cigarettes or equivalent per day from Screening up to Enrollment, and is unable to be restricted to  $\leq 5$  cigarettes per day and for 6 h post dose during their period of residence in the clinical unit
7. Concomitant use of medications known to affect the elimination of serum creatinine (eg, trimethoprim or cimetidine) and inhibitors of renal tubular secretion (eg, probenecid) within 60 d of Day -2
8. History or presence of an abnormal ECG, which, in the investigator's opinion, is clinically significant and/or a QT interval corrected for heart rate using Fridericia's formula (QTcF)  $\geq 450$  milliseconds (ms) and  $\geq 470$  ms for healthy male and female subjects, respectively, and  $> 500$  ms for subjects with HI at Screening
9. Consumption of alcohol-within 72 h prior to Check-in and caffeine-containing beverages within 48 h prior to Check-in and during confinement
10. Consumption of more than 28 units of alcohol per wk for males or 14 units of alcohol per wk for females, where 1 unit of alcohol equals one-half pint of beer, 4 ounces (oz) of wine, or 1 oz of spirits, or significant history of alcoholism or drug/chemical abuse within the last 2 y
11. Positive serology for HBsAg and anti-HCV (healthy subjects), HAV immunoglobulin M, or anti-HIV Type 1 and Type 2 (all subjects)
12. Loss of more than 450 mL blood during the 3 mo before the trial (eg, as a blood donor)
13. Current enrollment in or have not yet completed at least 30 d or 5 elimination half-lives, whichever is longer, since receiving an investigational device or product, or receipt of other investigational agents within 30 d of pexidartinib
14. History of any malignancy (except basal cell carcinoma) in the past 5 y

15. In the opinion of the investigator, history of a clinically significant illness within 4 wk prior to administration of study drug
16. Participation in a previous pexidartinib study
17. Employment by the clinic or the Sponsor
18. Any other reason, in the opinion of the investigator, which precludes subject participation in the study
19. Familial relationship with another study participant

Additional Exclusion Criteria for Matched Healthy Subjects:

1. Any clinically relevant abnormality identified on the physical examination, ECG, vital signs, or laboratory tests at Screening.
2. Any clinically unstable, uncontrolled medical condition.
3. Liver function (AST, ALT, alkaline phosphatase of liver origin, and TBIL) test results above the upper limit of normal at Screening and on Day -2.
4. Use of any prescription or over-the-counter (OTC) medications (systemic or topical), vitamins, or dietary/herbal supplements within 14 d prior to study drug dosing, with the exception of acetaminophen ( $\leq 2$  g/d), stool softeners, and topical hydrocortisone cream, which are permitted.

Additional Exclusion Criteria for Subjects with Hepatic Impairment:

1. Any clinically unstable, uncontrolled medical conditions other than those associated with HI.
2. Evidence of infection with HBV and/or new or acute HCV infection within the preceding 6 mo.
3. HI subjects maintained on a gastric pH modifier (eg, proton pump inhibitor), must be discontinued from this medication 7 d prior to and 24 h after pexidartinib administration. The subject should be switched to Gelusil (aluminum hydroxide, magnesium hydroxide, and simethicone) as needed for up to 48 h prior to the administration of pexidartinib. Gelusil use is prohibited from 48 h prior to the administration of pexidartinib to 24 h post pexidartinib dosing. At 24 h post pexidartinib, treatment with the usual gastric pH modifier can be resumed.
4. HI subjects maintained on oral or transdermal hormone replacement therapy for postmenopausal symptoms in females or hypogonadism in men are excluded from participating unless they have been discontinued for at least 28 d prior to pexidartinib administration and for 7 d post pexidartinib. Other hormonal replacement therapy for maintenance of chronic conditions (eg, insulin, thyroxin) is permitted. Oral contraceptives are permitted in women of childbearing potential.
5. Subjects with active Stage 3 or Stage 4 encephalopathy
6. Fluctuating or rapidly deteriorating hepatic function as indicated by recent history or worsening of clinical and/or laboratory signs of HI as judged by the investigator.

